### **Phase 3:**

**Purpose:** to assess safety and efficacy of the device over 24 hours in comparison to venous blood glucose and interstitial fluid (ISF) glucose using iPro2 in 20 subjects with type 1 diabetes as inpatients.

#### **Primary outcome:**

- Correlation with venous blood glucose & ISF glucose (iPro2–Medtronic, Northridge, California)

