#### 4. Trial Objectives and Purpose

This trial assesses the safety and efficacy of the Imperial Microprobe array biosensor for continuous monitoring of ISF glucose.

Safety will be assessed in relation to skin inflammation, skin damage, risk of fracture of microprobe tips within skin layers and pain. This will be assessed over six hours initially then over 24 hours in non-diabetic volunteers then over 24 hours in subjects with type 1 diabetes as in-patients and finally, in ambulatory situation over 5 days.

Efficacy will be assessed mechanically (ability to penetrate stratum corneum) and functionally (ability to sense ISF analytes). Functional efficacy of microprobe arrays to continuously monitor ISF glucose will be assessed in comparison to venous blood glucose levels and ISF glucose using iPro2 in as inpatients (phase3) then in an ambulatory state (phase 4).

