#### **Secondary outcomes:**

- Clarke error grid
- Skin inflammation
- Skin penetration
- Pain score
- Acceptability questionnaire
- Magnitude of current

**Subject inclusion criteria** Subjects may be recruited if:

- Adults over 18 years of age
- Diagnosed with Type 1 diabetes for greater than 1 year
- HbA1c less than or equal to 9.0 % (75 mmol/mol)
- Registered with a GP

**Subject exclusion criteria** Subjects are excluded if:

- History of diabetic dermopathy or pre-existing skin condition
- History of upper limb neuropathy or radiculopathy
- Pregnant or planning pregnancy in next 12 months
- Breastfeeding
- Enrolled in other clinical trials
- uncontrolled concurrent illness
- physical or visual impairment preventing sensor's use
- Have active malignancy or under investigation for malignancy

**Subject withdrawal criteria** Subjects will be withdrawn from the study in the case of:

1. Loss of capacity to give informed consent
2. Development of diabetic neuropathy, dermopathy or other skin conditions
3. Terminal illness

Withdrawal will be immediate and subjects will be followed up in the appropriate out-patient diabetes clinic within 4 weeks of withdrawal.

Recruiting will be undertaken in the diabetes clinics at St. Mary's Hospital and Charing Cross Hospital campuses of Imperial College Healthcare NHS Trust. Participant information sheets will be given to

potential subjects and, after a minimum of 48 hours and following any questions, informed consent will be taken.

Usual care will be maintained for diabetes throughout the study. No concomitant medical therapies are contra-indicated.

Subjects will be asked not to apply any cosmetic formulations on the non-dominant forearm for 7 days prior to the study.

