#### **Phase 4 (visit 2):**

**Purpose:** to assess ambulatory efficacy and lifetime of the microprobe array sensor over 5 days in continuous ISF glucose monitoring in comparison to iPro2 in 20 subjects with type 1 diabetes

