#### **Primary outcome:**

- Correlation with ISF CGM (iPro2 – Medtronic)

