#### **Visit:**

- On the morning of the visit, subjects will be instructed to have their standard breakfast and to adhere to their usual practice of diabetes management; this will be maintained throughout the study period.
- Attend the Wellcome Trust-Sir John McMichael Clinical Research Facility at the Hammersmith Hospital campus of Imperial College between 9:00 - 10:00 am
- Between 10:00 – 11:00, microprobe array and iPro2 device will be implanted in each subject.
- The outer margin of a 2 cm^2 skin area on the ventral aspect of the non-dominant forearm will be marked before the application of sterile microprobe array to the center of this skin area. The marked skin area will be shaved if hairy. Microprobe insertion will be achieved by applying gentle pressure. Microprobe array will be secured in place using adhesive plaster for 24 hours with 5 minutes sampling as moving average of 1 minute intervals.

- Medtronic iPro2 (Northridge, California) retrospective/blinded continuous glucose monitoring sensor will be implanted in the anterior abdominal wall and calibrated as per manufacturer's instructions.
- Subjects will be allowed to go home with advice to have normal daily activity with no alteration to their insulin doses or other aspects of diabetes management. Subjects will be asked to keep a food diary and a diary for self-monitored blood glucose levels.
- Subjects will attend the research unit on day 6 between 9:00-10:00. The 2 devices will be removed. Skin area around the microprobe array will be inspected by a doctor for any evidence of skin inflammation using a 4-point scale (none, mild, moderate and severe). This will be compared to skin area around iPro2 sensor insertion site.
- Following removal of the device, the microprobe treated skin area will be examined using confocal microscopy imaging technique to confirm penetration and examine the created microchannels.
- Microprobe arrays will be examined for integrity before and after application using SEM.
- Visual analogue scale (VAS) will be used to assess pain resulting from microprobe insertion in comparison with pain resulting from blood sampling and pain resulting from insertion of iPro2 sensor.
- At the end of the 5 days ambulatory period, subjects will be asked to fill a validated acceptability questionnaire.

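### Correlation is the only primary outcome in Phases 3 and 4, so a scale or offset error shared by all arrays cannot show in the headline efficacy result

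*Protocol*

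**What the plan says.** Section 5 lists one primary outcome for each of the two phases in people with type 1 diabetes. For Phase 3 it is "Correlation with venous blood glucose & ISF glucose", the latter measured by iPro2. For Phase 4 it is "Correlation with ISF CGM", again iPro2. The "Clarke error grid" is a secondary outcome in both phases. Neither list contains bias, MARD or limits of agreement.

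The efficacy aim is comparison with reference glucose. Section 4 states: "Functional efficacy of microprobe arrays to continuously monitor ISF glucose will be assessed in comparison to venous blood glucose levels", and names iPro2 as well. The Phase 3 purpose is to assess the device "in comparison to venous blood glucose and interstitial fluid (ISF) glucose using iPro2". The Phase 4 purpose concerns "continuous ISF glucose monitoring in comparison to iPro2".

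For the reference data, Phase 3 takes 40 venous samples per subject for YSI analysis. The Phase 4 visit describes no venous sampling. There the iPro2 sensor "will be implanted in the anterior abdominal wall and calibrated as per" the manufacturer's instructions, and the protocol adds: "Subjects will be asked to keep a food diary and a diary for self-monitored blood glucose levels".

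**The concern.** Whether a glucose sensor works depends on how close its readings are to the true values. Correlation answers a narrower question: do the readings rise and fall in a straight-line relation with the reference? A sensor that is wrong by a fixed factor or a fixed amount in every subject can still have r close to 1.

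The protocol itself describes an error of this type. Section 1 puts interstitial glucose at about 60% of blood glucose and gives this as a reason why existing sensors need calibration. Section 5 describes calibration for iPro2 but states no such step for the array. The size of any gain error in this array is unknown, but the possibility is not remote.

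At stake is the main efficacy statement of both phases. It could look excellent for a sensor with a large systematic error, and the error would then appear only in a secondary outcome.

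**Working it through.** **Inputs from the protocol.** 20 subjects in each phase. In the Phase 3 visit, venous samples every 30 minutes from 11:00 to 22:00 (23, both ends counted), then hourly to 07:00 (9 more), then every 30 minutes to 11:00 (8 more): 23 + 9 + 8 = 40, as stated. At 2.5 mL each this is 100 mL, also as stated. Pairs available: 20 × 40 = up to 800. The protocol gives no figure for sensor error or for the glucose distribution, so those below are assumptions.

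**Step 1: the identity.** For any offset a and any gain b > 0, corr(X, a + bY) = corr(X, Y). No distributional assumption is needed. Rank correlation is equally unchanged.

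**Step 2: a noise-free sensor reading 0.6 × reference.**
- r = 1.00.
- MARD = |0.6 − 1| = 40%.
- Mean bias = −0.4 × mean glucose: −3.2, −3.6 and −4.0 mmol/L at assumed means of 8, 9 and 10 mmol/L.
- Clarke zone A requires a reading within 20% of reference, or both values below 3.9 mmol/L. A 40% error never meets the first condition, so zone A is the share of reference values below 3.9. For a lognormal distribution with mean 9 and SD 3.5 this is 2.0%. Over means of 8 to 10, SDs of 2.5 to 4 and three distribution shapes (lognormal and two truncated normals) it is 0.5% to 10.5%.
- Over the same grid, zones A and B together hold 84% to 98%, and zone D holds 2% to 16%.

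**Step 3: a noisy sensor, simulated.** 20 subjects × 40 pairs; mean glucose 9 mmol/L, between-subject SD 1.5, within-subject SD 3.2, values held to 2.5–22 mmol/L; noise SD 1.0 mmol/L. One gain and one offset (mmol/L) apply to all arrays.

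| Gain | Offset | r | Bias (mmol/L) | MARD | Zone A |
|---|---|---|---|---|---|
| 1.0 | 0 | 0.950 | 0.00 | 11.3% | 86.8% |
| 0.8 | 0 | 0.950 | −1.77 | 21.0% | 53.5% |
| 0.6 | 0 | 0.950 | −3.54 | 40.0% | 8.4% |
| 1.3 | 0 | 0.950 | +2.66 | 31.7% | 26.8% |
| 1.0 | +2 | 0.950 | +2.00 | 27.6% | 42.0% |
| 1.0 | −2 | 0.950 | −2.00 | 27.2% | 50.7% |
| 1.0 | +3 | 0.950 | +3.00 | 41.0% | 14.9% |

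Spearman's coefficient was 0.949 in every row.

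**Step 4: where the claim stops.** If each array has its own gain, pooled r does fall. With noise-free gains centred at 0.6 and a log-SD of 0, 0.1, 0.2 or 0.3 between arrays, pooled r is 1.00, 0.97, 0.88 or 0.78. MARD stays at 40%, 40%, 39% and 38%. The r computed within each subject is 1.00 throughout, so it misses even an error specific to one array, provided the error is fixed.

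**The case against.** **The aim may be more modest.** Section 4 describes functional efficacy as the ability to sense interstitial analytes, and the magnitude of the current is itself an outcome. Whether the signal follows glucose is a fair first question, and correlation suits it. That argument fits Phase 1, which is labelled proof of concept. Phases 3 and 4 are defined by comparison with reference glucose, and the Clarke grid listed for them already requires array readings in glucose units.

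**Calibration would remove a fixed gain.** It might, but no such step for the array is stated, and an agreement measure is what would show whether it had worked. One part of this objection stands: if the array is not calibrated to blood, its difference from venous glucose partly reflects physiology. The report must therefore say what the readings are scaled to.

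**Correlation does respond to drift and to differences between arrays.** Both are true, and drift bears on the sensor-lifetime aim of Phase 4. This is a reason to keep correlation, not to rely on it alone.

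**The Clarke grid already covers the bias.** It would reveal it, including through zone D. The criticism is therefore limited to the primary result.

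**This is a small, unpowered early study with no test attached to the primary label.** This stands and limits the weight of the point. The choice of coefficient, pooled or per-subject calculation, and any pass mark may be settled in an analysis plan that is not at hand, and are not counted as faults here. A concordance coefficient would respond to bias (0.949 falls to 0.455 at gain 0.6), but the protocol says only correlation.

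**Conclusion.** The concern holds. In both phases the only primary outcome is blind to a scale or offset error common to all arrays. That follows from an identity and rests on no assumption beyond correlation meaning an ordinary Pearson or Spearman coefficient. How large an error could go unseen is illustrated, not predicted: under the stated assumptions, r stays at 0.950 while MARD ranges from 11.3% to 41.0% and zone A from 86.8% down to 8.4%. The bias would not be lost altogether, because the Clarke grid is planned. It would be missing from the result by which each phase is judged. This should be corrected; it does not invalidate the data collection.

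**What to change.** In the Phase 3 and Phase 4 outcome lists, make agreement primary: MARD, reported with Bland-Altman bias and limits of agreement.

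- **Phase 3:** against YSI venous glucose, and also against iPro2.
- **Phase 4:** against iPro2, with a statement that iPro2 is itself a calibrated sensor and not a laboratory standard. Use the self-monitored glucose diary as support only, since its frequency is not fixed.
- **Both phases:** allow for repeated pairs within a subject, by summarising each subject first and then across the 20, or by a mixed model with a subject effect. State whether and how the array is calibrated, and leave out any pairs used for it.
- **Secondary outcomes:** keep correlation, saying whether it is pooled or per subject. Keep the Clarke grid, with zone A shown apart from zone B, because A and B together can exceed 80% even at a gain of 0.6.

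The cost is a change of wording in the two outcome lists and in section 10. No extra subjects, visits or samples are needed, and the sample size does not rest on a power calculation for correlation. The likely price is a less flattering headline figure.

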#### **Secondary outcomes:**

- Clarke error grid
- Skin inflammation
- Skin penetration
- Pain score
- Acceptability questionnaire
- Magnitude of current

**Subject inclusion criteria** Subjects may be recruited if:

- Adults over 18 years of age
- Diagnosed with Type 1 diabetes for greater than 1 year
- HbA1c less than or equal to 9.0 % (75 mmol/mol)
- Registered with a GP

**Subject exclusion criteria** Subjects are excluded if:

- History of diabetic dermopathy or pre-existing skin condition
- History of upper limb neuropathy or radiculopathy
- Pregnant or planning pregnancy in next 12 months
- Breastfeeding
- Enrolled in other clinical trials
- uncontrolled concurrent illness
- physical or visual impairment preventing sensor's use
- Have active malignancy or under investigation for malignancy

**Subject withdrawal criteria** Subjects will be withdrawn from the study in the case of:

1. Loss of capacity to give informed consent
2. Development of diabetic neuropathy, dermopathy or other skin conditions
3. Terminal illness

Withdrawal will be immediate and subjects will be followed up in the appropriate out-patient diabetes clinic within 4 weeks of withdrawal.

Recruiting will be undertaken in the diabetes clinics at St. Mary's Hospital and Charing Cross Hospital campuses of Imperial College Healthcare NHS Trust. Participant information sheets will be given to

potential subjects and, after a minimum of 48 hours and following any questions, informed consent will be taken.

Usual care will be maintained for diabetes throughout the study. No concomitant medical therapies are contra-indicated.

Subjects will be asked not to apply any cosmetic formulations on the non-dominant forearm for 7 days prior to the study.

#### **Visit 1:**

- On the morning of the visit, subjects will be instructed to have their standard breakfast and to adhere to their usual practice of diabetes management, this will be maintained throughout study period.
- Attend the Wellcome Trust-Sir John McMichael Clinical Research Facility at the Hammersmith Hospital campus of Imperial College between 9:00 - 10:00 am.
- Between 10:00 – 11:00; subjects will undergo routine clinical examination, have venous blood taken for HbA1c, lipids, creatinine, liver function tests, FBC following an intravenous cannula insertion and female subjects of childbearing age will have a urine pregnancy test performed. This will be followed by insertion of microprobe array and iPro2 device in each subject.
- The outer margin of a 2 cm^2 skin area on the ventral aspect of the non-dominant forearm will be marked before the application of sterile microprobe array to the center of this skin area. The marked skin area will be shaved if hairy. Microprobe insertion will be achieved by applying gentle pressure. Microprobe array will be secured in place using adhesive plaster for 24 hours with 5 minutes sampling as moving average of 1 minute intervals.
- Medtronic iPro2 (Northridge, California) retrospective/blinded continuous glucose monitoring sensor will be implanted in the anterior abdominal wall and calibrated as per manufacturer's instructions.
- An 18-G intravenous cannula will be inserted in the non-dominant upper limb for venous sampling. 2.5 mL venous blood will be taken at 30 minutes intervals between 11:00 - 22:00 the at 60 minutes intervals between 22:00 – 7:00 then back to 30 minutes intervals between 7:00 – 11:00. Venous blood samples will be distributed for venous blood glucose using YSI analyser. Thus, in total, 40 venous samples will be withdrawn from each subject. Maximum blood volume collected over study visit duration is 100mL.
- A 60g CHO meal will be provided between 12:00 – 13:00.
- A 20 g CHO snack will be provided between 15:00 – 16:00 (optional).
- A 60 g CHO meal will be provided between 18:00 – 19:00.
- A 20 g CHO snack will be provided between 22:00 – 23:00 before sleep (optional).
- A 40 g CHO meal will be provided between 7:00 – 8:00.
- At 11:00, devices and intravenous catheter will be removed.

- Skin area around the microprobe array will be inspected at 1, 2, 6 hours post-insertion and after removal of the device at 24 hours by a doctor for any evidence of skin inflammation using a 4-point scale (none, mild, moderate and severe). This will be compared to skin area around iPro2 sensor insertion site.
- Following removal of the device at 24 hours, the microprobe treated skin area will be examined using confocal microscopy imaging technique to confirm penetration and examine the created microchannels.
- Microprobe arrays will be examined for integrity before and after application using SEM.
- Visual analogue scale (VAS) will be used to assess pain resulting from microprobe insertion in comparison with pain resulting from blood sampling and pain resulting from insertion of iPro2 sensor.
- At the end of the 24 hour period, subjects will be asked to fill a validated acceptability questionnaire.

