**Visit:**

- Attend the Wellcome Trust-Sir John McMichael Clinical Research Facility at the Hammersmith Hospital campus of Imperial College between 9:00 - 10:00 am. Female subjects of childbearing age will have a urine pregnancy test performed.
- The outer margin of a 2 cm^2 skin area on the ventral aspect of the non-dominant forearm will be marked before the application of sterile microprobe array to the center of this skin area. The marked skin area will be shaved if hairy. Microprobe insertion will be achieved by applying gentle pressure. Microprobe array will be secured in place with an adhesive plaster for six hours with 5 minutes sampling as moving average of 1 minute intervals.
- An 18-G intravenous cannula will be inserted in the non-dominant upper limb for venous sampling. Throughout the 6 hours, 2.5mL venous blood will be taken at 15 minutes interval and will be distributed for venous glucose estimation using YSI analyser. Maximum blood volume collected over study visit duration is 60mL.
- Six hours after microprobe insertion (at 16:00), the microprobe array and intravenous cannula will be removed.
- Skin area around the microprobe array will be inspected at 1, 2 hours post-insertion and after device removal by a doctor for any evidence of skin inflammation using a 4-point scale (none, mild, moderate and severe).
- Following removal of the device, the microprobe treated skin area will be examined using confocal microscopy imaging technique to confirm penetration and examine the created microchannels.
- Microprobe arrays will be examined for integrity before and after application using scanning electron microscopy (SEM).
- Visual analogue scale (VAS) will be used to assess pain resulting from microprobe insertion in comparison with pain resulting from blood sampling.

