## 6. Methodology

Non-randomised open label study

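### The within-subject pain comparison does not balance procedure order: Phase 3 puts the cannula before the array in everyone, and the array-iPro2 order in Phases 3 and 4 is left open

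*Protocol*

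**What the plan says.** Pain score is a secondary outcome in all four phases (Protocol, section 5). In Phases 1 and 2 the VAS is to rate "pain resulting from microprobe insertion in comparison with pain resulting from blood sampling". In Phases 3 and 4 array insertion is rated "in comparison with pain resulting from blood sampling and pain resulting from insertion of iPro2 sensor".

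On the order of procedures, the protocol says the following:

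- **Phase 3, Visit 1.** Between 10:00 and 11:00 subjects "have venous blood taken for HbA1c, lipids, creatinine, liver function tests, FBC following an intravenous cannula insertion", and then: "This will be followed by insertion of microprobe array and iPro2 device in each subject". A later bullet, after those for the array and the iPro2, adds: "An 18-G intravenous cannula will be inserted in the non-dominant upper limb for venous sampling". It is not said whether this is the same cannula.
- **Phase 4, Visit.** "Between 10:00 – 11:00, microprobe array and iPro2 device will be implanted in each subject". No cannula or venous sample is scheduled.
- **Phases 1 and 2, Visit.** The array bullet stands before the cannula bullet, with no word that makes the two a sequence.

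Section 6 describes a "Non-randomised open label study". No section randomises or balances the order of insertion, and none says when each VAS is completed or which blood sample is rated.

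**The concern.** A pain rating can depend on what the subject has just been through. A preceding needle may make the next procedure seem milder by contrast, or habituation or sensitisation may change the rating. When every subject meets the procedures in the same order, any such effect goes in full into the mean paired difference, and nothing in the data can separate it from the difference between devices.

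This has to be settled in the protocol, because an analysis plan written later cannot estimate an order effect that the design never varied. Pain is also not incidental here: section 4 names it in the safety objective, and the background presents the technology as less painful. The scale is subjective and there is no masking.

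**Working it through.** The protocol gives no alpha, SD, effect size or power for pain, so there is no stated figure to reproduce.

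**1. What is fixed and what is open**

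| Contrast | Phase | Order in the text |
|---|---|---|
| Array vs first cannulation and draw | 3 | Cannula and draw first, every subject |
| Array vs iPro2 | 3 and 4 | Unstated: the two are joined only by *and* |
| Array vs cannula | 1 and 2 | Unstated: bullets only |
| Array vs blood sampling | 4 | Comparison named, but no sampling scheduled |

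Bullet position is not evidence of sequence. Phase 3's bullets also run array, iPro2, 18-G cannula, although its text puts a cannula first. In Phases 1 and 2 the skin inspections at 1 and 2 hours are listed after the bullet on array removal.

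The rated sampling event is open as well. In Phase 3, after the first draw, there are 23 samples from 11:00 to 22:00, 9 from 23:00 to 7:00 and 8 from 7:30 to 11:00. That makes 23 + 9 + 8 = 40, matching the stated total, and any of them could be the comparator.

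**2. Can device and order be separated?** Take a within-subject model with 20 subject columns, one device column and one order column, 22 in all.

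- One order for everyone: rank 21 of 22. Device and order are aliased.
- Ten subjects in each order: rank 22 of 22. Both can be estimated.

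**3. Bias in the mean difference.** Let δ be the true device difference, e the shift caused by order, and p the proportion of subjects with the array first. The expected mean paired difference is δ + (2p − 1)e.

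- p = 1 or p = 0: the full shift e remains, with sign + or −.
- p = 0.75, say through unplanned staff habit: (2 × 0.75 − 1)e = 0.5e.
- p = 0.5: zero bias.

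**4. Illustration only.** Assume n = 20, δ = 0, a single order, and a two-sided 5% paired t-test with 19 degrees of freedom. The non-centrality is (e/SD) × √20, and √20 = 4.472.

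| Assumed e, in SDs of the paired difference | Non-centrality | Rejection rate |
|---|---|---|
| 0.25 | 1.118 | 0.186 |
| 0.50 | 2.236 | 0.565 |
| 0.75 | 3.354 | 0.889 |

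On a 100 mm scale with an assumed SD of 20 mm, the first two rows are shifts of 5 mm and 10 mm, with a standard error of 20/4.472 = 4.5 mm.

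**5. After balancing.** With 10:10 order and an order term, 20,000 simulated trials per setting gave rejection rates of 0.049 to 0.051 for the same three shifts. The error degrees of freedom fall from 19 to 18.

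**The case against.** The case against is substantial. Only one order is documented, cannula before array in Phase 3. Pain is secondary throughout, and section 10 disclaims comparison groups and any powering against usual care. No test on pain is declared, so the rejection rates describe an analysis that the protocol does not promise, on assumed inputs. The details of VAS timing are commonly left to an analysis plan or case report form. All of this limits the weight of the point. It does not remove it: the pain comparison is prescribed, and a descriptive mean difference carries the same order bias as a test.

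Several stronger readings are tempting but not supported:

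- *The array always precedes the iPro2.* The text names the two together and gives no order. The fault is lack of control, not a fixed sequence.
- *Phases 1 and 2 run array then cannula and Phase 3 reverses this, so a shift in relative pain between volunteers and patients could be an order effect.* This rests on bullet position, which Phase 3's own text contradicts. Nor is such a between-phase comparison an outcome in any phase.
- *The VAS is taken late, after removal.* This again rests on bullet position. The time of rating is simply not given.
- *The bias favours the array.* Contrast, habituation and sensitisation are all possible, and the documents give no direction.
- *Using one array-cannula order in every phase would cure the problem.* It would make the phases consistent but leave that contrast fully confounded.

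**Conclusion.** The point holds in a limited form. The order of procedures in a prescribed within-subject pain comparison is not balanced. For array against the first cannulation and draw in Phase 3, order is fixed for all 20 subjects. If that event is the one rated, the contrast cannot be separated from order. For array against iPro2 in Phases 3 and 4 the order is uncontrolled, and the bias could be anything from none to the full order effect, depending on what staff happen to do. For Phases 1 and 2 nothing can be concluded about the order.

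The size is unknown. The rates of 19% to 89% rest wholly on an assumed 5% test and assumed shifts of 0.25 to 0.75 SD, and show only that a modest effect would matter at this sample size. No primary outcome is affected. This is a cheap improvement to a secondary comparison, not a threat to the trial.

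**What to change.** 1. **Array against iPro2, Phases 3 and 4.** Take the insertion order from a list prepared in advance: 10 subjects array first, 10 iPro2 first, with the order reversed for the same subject at the Phase 4 visit. Record the order actually used.
2. **VAS timing.** Record each score immediately after its own insertion and before the next procedure.
3. **Analysis.** Analyse array minus iPro2 as a paired difference with an order term.
4. **Array against blood sampling.** State which sampling event is rated in each phase, including what is meant in Phase 4, where none is scheduled. Reconcile the Phase 3 visit text on whether one or two cannula insertions are intended, and when. Where the cannula always comes first, report this contrast as descriptive and confounded with order.

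The cost is a 20-line list, a few sentences in the visit schedule and one degree of freedom. Both devices already go in within the same hour, so no extra subjects or visits are needed. The list does not repair the blood-sampling contrast, which is why item 4 asks only for definition and cautious reporting.

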## 7. Timescale

It is anticipated that the studies will take place over 4 years. Non-diabetic subjects will be recruited to the study for phase 1 and 2 (2 visits). Subject with type 1 diabetes will be recruited for phases 3 and 4 of the study for up to 12 - 18 months, with a total of 2 visits in that timeframe.

**8. Potential risks and benefits** The potential risks and burdens for research participants are as follows:

Skin inflammation may occur with the use of microprobe arrays. A literature review shows this to be minimal and transient. Subjects will be examined regularly by a doctor to assess the degree of any inflammatory reaction and the need for any intervention (ending the study or the use of local/systemic therapy if required).

Pain may result from microprobe array insertion. A literature review shows this to be absent or very minimal when compared to traditional needles or lancets. The array will be inserted with gentle manual pressure and pain score will be assessed in phases 2, 3 and 4.

In all visits (excluding phase 4) there is either a venous blood test or insertion of an intravenous cannula. These have the potential to cause discomfort. This will be minimised by experienced research personnel performing the procedure and appropriate use of equipment and aseptic technique.

In phases 3 and 4, subjects will have a continuous glucose-monitoring sensor (iPro2, Medtronic) inserted in anterior abdominal wall subcutaneous tissue. Sensor insertion can be associated with some discomfort but the insertion devices are spring-loaded with introducers, making the process rapid and often painless. Any discomfort will be minimised by adhering to manufacturer's instructions.

Assessment of efficacy of the device will be in comparison to venous glucose levels and a commercially available continuous glucose sensor over a period of twenty-four hours as in-patients. 2.5 mL venous blood will be taken at 30 minutes intervals apart from the period between 11:00 - 22:00 when the blood will be taken hourly.

During studies involving subjects with type 1 diabetes, subjects will adhere to their usual practice of diabetes management.

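### Phase 3 venous sampling is given as two opposite schedules, and the stated 100 mL visit maximum leaves nothing for the baseline bloods

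*Protocol*

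**What the plan says.** Section 5, Phase 3, Visit 1 is the visit procedure. It sets the daytime frequency, "2.5 mL venous blood will be taken at 30 minutes intervals between 11:00 - 22:00", and then the rest of the 24 hours, "60 minutes intervals between 22:00 – 7:00 then back to 30 minutes intervals between 7:00 – 11:00". It closes with a count and a volume: "Thus, in total, 40 venous samples will be withdrawn from each subject. Maximum blood volume collected over study visit duration is 100mL".

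An earlier bullet of the same visit, timed between 10:00 and 11:00, requires participants to "have venous blood taken for HbA1c, lipids, creatinine, liver function tests, FBC". No volume is given for that draw.

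Section 8 (Potential risks and benefits) describes the comparison with venous glucose and a commercial sensor "over a period of twenty-four hours as in-patients". It gives the sampling as "30 minutes intervals apart from the period between 11:00 - 22:00 when the blood will be taken hourly".

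The Phase 3 primary outcome is "Correlation with venous blood glucose & ISF glucose", the interstitial reference being iPro2.

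**The concern.** Both sections name the 11:00 to 22:00 window and give it opposite frequencies, so no single timetable satisfies both. Section 8 can only mean Phase 3, because that is the only phase with a 24-hour in-patient stay, venous glucose and a commercial sensor together. Nothing elsewhere in the protocol settles the matter.

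Two things are at stake. First, the sampling times decide when a venous reference value exists to pair with the sensor reading, and venous glucose is one of the two references for the Phase 3 primary outcome. The 11:00 to 22:00 window contains both 60 g carbohydrate meals, so its density matters for how many pairs fall around them. Second, section 8 is where the protocol states the burden on participants, and it differs from the procedure on how often blood is taken overnight.

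The volume is a separate point. The figure is worded as a maximum for the whole visit, but it appears to be fully used by the glucose samples alone.

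**Working it through.** **Inputs.** 2.5 mL per glucose sample and the two timetables, from section 5 (Phase 3, Visit 1) and section 8. The stated figures are 40 samples and 100 mL. The number of Phase 3 participants, 20, is from the Phase 3 purpose statement.

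**Method.** List the scheduled times from 11:00 to 11:00 the next day, include both end points, count each shared boundary once, and multiply by 2.5 mL.

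**Step 1: reproduce the stated figure from the Visit 1 timetable.**
- 11:00 to 22:00, half-hourly: 11 h × 2 + 1 = 23
- 23:00 to 07:00, hourly: 9
- 07:30 to 11:00, half-hourly: 8
- Total: 23 + 9 + 8 = 40 samples; 40 × 2.5 = 100 mL

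Both stated figures are reproduced exactly.

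**Step 2: the section 8 timetable.**
- 11:00 to 22:00, hourly: 11 + 1 = 12
- 22:30 to 07:00, half-hourly: 18
- 07:30 to 11:00, half-hourly: 8
- Total: 12 + 18 + 8 = 38 samples; 38 × 2.5 = 95 mL

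**Step 3: compare the times themselves.**

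| Period | Visit 1 | Section 8 | Shared |
|---|---|---|---|
| 11:00 to 22:00 | 23 | 12 | 12 |
| after 22:00 to 07:00 | 9 | 18 | 9 |
| after 07:00 to 11:00 | 8 | 8 | 8 |
| Total | 40 | 38 | 29 |

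Eleven times occur only in Visit 1 (40 − 29) and nine only in section 8 (38 − 29). Over 20 participants with complete sampling, that is 20 × 23 = 460 against 20 × 12 = 240 daytime samples, and 20 × 9 = 180 against 20 × 18 = 360 overnight.

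**Step 4: room for the baseline bloods.** Let V be their volume in mL, which is not stated.
- Visit 1 timetable: total = 100 + V. Room within the stated maximum: 100 − 100 = 0 mL, so any V above zero exceeds it.
- Section 8 timetable: total = 95 + V. Room: 100 − 95 = 5 mL, so the maximum is exceeded once V is above 5 mL.

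Purely as an illustration, an assumed V of 5 to 20 mL gives 105 to 120 mL under Visit 1 and 100 to 115 mL under section 8. These are not the protocol's figures.

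**The case against.** The strongest reply to the first part is that section 8 contains a drafting slip. Visit 1 is the operational procedure, and its timetable, count and volume agree with one another. Section 8 is one narrative sentence with neither a count nor a volume. Site staff working from Visit 1 have a complete schedule, and the totals differ by only 2 samples and 5 mL. This limits the weight of the point but does not remove it: the distribution over the day differs far more than the total. A reader might also infer from the internal agreement that the Visit 1 schedule is the intended one. Agreement with its own count shows only that the section is self-consistent, and the protocol does not say which section governs.

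On the volume, it can be said that the 100 mL closes the glucose-sampling bullet and may have been meant as the total for that series. That may explain how the figure arose, but the wording covers the whole visit, so the text as it stands is wrong or at least loose. The objection is right that the excess cannot be sized. It is also right that the protocol ties 100 mL to no safety threshold, so a reader should not infer that a safety limit is breached.

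A reader might further infer that the Phase 1 and Phase 2 volumes are wrong, because the 40 samples in Phase 3 count both end points. The document does not support this. Phase 1 reads "Throughout the 6 hours, 2.5mL venous blood will be taken at 15 minutes interval"; samples from 15 minutes to 6 hours number 6 × 4 = 24, and 24 × 2.5 = 60 mL, as stated. Phase 2 adds one next-day sample: 60 + 2.5 = 62.5 mL, as stated. Nothing requires one end-point convention across phases of different design. Nor does the Phase 2 total show that laboratory bloods are meant to be counted, since its extra draw is itself a glucose sample.

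**Conclusion.** Two defects stand, both in Phase 3.

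- **The schedules contradict each other.** The mismatch is 40 against 38 samples in total, but 23 against 12 by day and 9 against 18 overnight, with 29 times in common. The counts rest only on including both 11:00 end points, which the stated 40 requires.
- **The stated visit maximum does not cover the blood the same visit requires.** Under the schedule that yields the stated 40 samples, it is exceeded by exactly the baseline volume, whose size cannot be known from the document.

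The consequence is moderate. It would overstate the case to say that the primary outcome is undermined: the iPro2 reference is unaffected, and either timetable supplies venous values across the 24 hours. What is lost is a single definition of when those values are taken, and an accurate statement of burden and blood volume.

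**What to change.** Reconcile section 5 (Phase 3, Visit 1) and section 8 to one venous sampling schedule. Which schedule is for the sponsor and the investigators to decide; this review does not choose. From that schedule, restate the number of samples and the maximum blood volume for the visit, with the baseline laboratory bloods included and their volume given. Check that the participant information, which is not shown here, carries the same schedule and volume.

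The cost is a text amendment in two places. Design, sample size and the Phase 1 and Phase 2 text do not need to change.
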